9.3.1. Analysis by Cohort during Dose Escalation (Part A)

Safety and PK data will be transferred to Lilly at the end of each completed cohort. A summary of safety and PK data will be provided.

9.3.2. Interim Analyses

CCI [REDACTED]

Safety, PK, and PD data will be transferred to Lilly at the completion of dose escalation (Part A).

Safety, efficacy, PK, and PD data will be transferred to Lilly approximately every 3 months and/or at the completion of each tumor-specific expansion (Parts B, C, D, E, F, and G).

10. Informed Consent, Ethical Review, and Regulatory Considerations

10.1. Informed Consent

The investigator is responsible for ensuring that the patient understands the potential risks and benefits of participating in the study, including answering any questions the patient may have throughout the study and sharing in a timely manner any new information that may be relevant to the patient's willingness to continue his or her participation in the study in a timely manner.

The informed consent document will be used to explain the potential risks and benefits of study participation to the patient in simple terms before the patient is entered into the study and to document that the patient is satisfied with his or her understanding of the potential risks and benefits of participating in the study and desires to participate in the study.

The investigator is ultimately responsible for ensuring that informed consent is given by each patient or legal representative before the study is started. This includes obtaining the appropriate signatures and dates on the informed consent document prior to the performance of any protocol procedures and prior to the administration of study drug.

In this protocol, the term "informed consent" includes all consent and assent given by patients or their legal representatives.

10.2. Ethical Review

Lilly must agree with all informed consent documents before they are submitted to the IRB/ERB and are used at investigative sites(s). All informed consent documents must be compliant with the International Conference on Harmonisation guideline on Good Clinical Practice (GCP).

Informed consent obtained under special circumstances may occur only if allowed by local laws and regulations, and performed in accordance with a written process approved by Lilly.

The investigator will provide Lilly with documentation of IRB/ERB approval of the protocol and the informed consent document *before* the study may begin at the investigative site(s). Any member of the IRB/ERB who is directly affiliated with this study as an investigator or as site personnel must abstain from the review board's vote on the approval of the protocol. The IRB/ERB(s) will review the protocol as required.

The investigator will supply the following to the investigative site's IRB/ERB(s):

- the current IB and updates during the course of the study
- informed consent document
- relevant curricula vitae.

10.3. Regulatory Considerations

This study will be conducted in accordance with:

- 1) Consensus ethics principles derived from international ethics guidelines, including the Declaration of Helsinki and council for International Organizations of Medical Sciences (CIOMS) International Ethical Guidelines
- 2) The International Conference of Harmonisation (ICH) Good Clinical Practices (GCP) Guideline [E6]
- 3) Applicable laws and regulations

The investigator or designee will promptly submit the protocol to applicable ERB/IRB(s).

LY2835219 is being studied in the United States (US) under a US Investigational New Drug (IND) application. The US IND number is 106100.

Some of the obligations of the sponsor will be assigned to a contract research organization (CRO).

An identification code assigned by the investigator to each patient will be used in lieu of the patient's name to protect the patient's identity when reporting AEs and/or other trial-related data.

10.3.1. Investigator Information

Site-specific contact information may be provided in a separate document.

10.3.2. Protocol Signatures

After reading the protocol, each principal investigator will sign the protocol signature page and send a copy of the signed page to a Lilly representative.

| Vital Signs and Weight (Temperature, Pulse Rate, Blood Pressure, Respiratory Rate) | | X | | | | | | X | X | X | | X | X | |
| Height | | X | | | | | | | | | | | | |
| Chest X-ray ^b | X | | | | | | | | | | | | X ^h | |
| Performance Status | | X | | | | | | | | | | X | X | X |
| CTCAE CCI Grading | | X ^c | | | | | | X | | | X | | X | X ^d |
| Concomitant Medications | | X | | | | | | | | | X | | X | X |
| Tumor Measurement (Palpable and Visible) | | X | | | | | | | | | X | | X | X |
| ECG ^e | | X | X | X | X | | | X | | | | | | |
| LY2835219 Therapy ^f | | | X | | | X | X | X | X | X | | X | X | |
| Fulvestrant Therapy (Part G only) | | | | | | X ^q | | X ^r | | | X | | X | |
| Radiological Tumor Assessments | X | | | | | | | | | | | | X ^h | |
| Archived Tumor Samples ⁱ | | X | | | | | | | | | | | | |
| Tumor Biopsy | | X ^j | | | | | | X ^j | | | | | | |
| Hematology | | X | X | | | | X | X | X | | X | | X | X |
| Serum Chemistry ^k | | X | X | | | | X | X | X | | X | | X | X |
| Serum Cortisol (random) | | X | | | | | | | | | X | | X | |
| Lymphocyte Subset Analysis (CD3, 4, 8, and 19) | | X | | | | | | | | | X | | X | |

Study Schedule 1: Assessments for Parts A, B, C, D, E, F, and G (Continued)

| Cycle/Visit | Pre-study/ Visit 0 | | Cycle 1 | | | | | | | | Cycle 2 and Beyond | | Follow- Up ^o | | | |
|--|-----------------------|--|-----------------|-----------------|-----|----|----|---|---------|----------|-----------------------|----|----------------------------|---------------|-----------------------|--|
| | | | -28 to -4 | -14 to -4 | -3* | -2 | -1 | 1 | 8 ±2 | 15 ±2 | 22 ±2 | 28 | 29 | | | |
| Relative Day Prior to Day 1 of Cycle 1 | | | | | | | | | | | | | | 1 to 27 | 28 ±2 ^p | |
| Blood PK Sampling ^l | | | | | X | X | X | X | | X | X | X | X | | | |
| CSF PK Sampling ^{l,m} | | | | | X | | | | | X | | | | | | |
| Hair Follicle (PD sample) ^l | | | | | X | X | | | | X | | X | | | | |
| Skin Biopsy (PD sample) ^l | | | X ^c | | | | | | | X | | | | | | |
| DNA Genotyping Blood Sample (stored) | | | X ^c | | | | | | | | | | | | | |
| Record results for any tumor markers in clinical database, if applicable | X | | | | | | | | | | | X | | X | | |

Abbreviations: CSF = cerebrospinal fluid; CTCAE = Common Terminology Criteria for Adverse Events; ECG = electrocardiogram; PK = pharmacokinetic; PD = pharmacodynamic.

*= Day -3 in Cycle 1 has to be either on Monday or Tuesday only.

a Females with child bearing potential must have a negative serum pregnancy test within 3 days of the first dose of study drug (i.e., Day-6 to Day-4).

b Chest X-ray may be omitted in patients having a chest CT as part of their radiological tumor assessment. Radiological tumor assessment, including Chest X-ray, is performed at baseline (Day -28 to Day-4), then between Day 21 and Day 28 of every other cycle beginning with Cycle 2.

c Obtain only after study eligibility is confirmed.

[figure not shown]
d All drug- or procedure-related adverse events and serious adverse events should be followed until they resolve, are no longer considered to be drug- or procedure-related, become stable or return to baseline, the patient starts a new therapy, the patient dies, or the patient becomes lost to follow-up. Frequency of evaluation is left to the judgment of the investigator.

e A central ECGs (no replicates required) should be obtained at baseline (Day-14 to Day-4) and at the following time points during Cycle 1 only: pre-dose, 2 and 4 hrs post-dose on Day-3; both Day-2 and Day-1 (as close to PK sample collection as possible); predose, 2 and 4 hrs postdose on Day 15.

f For the once daily schedule, LY2835219 is to be administered every 24 hours on Days 1 through 28 of each cycle except in Cycle 1, when study drug will be administered as a single (morning) dose on Day -3 and then every 24 hours on Days 1 to 27. For the twice daily schedule, LY2835219 is to be administered every 12 hours on Days 1 through 28 of each cycle except in Cycle 1, when LY2835219 will be administered as a single (morning) dose on Day -3, every 12 hours on Days 1 to 27, and as a single (morning) dose on Day 28. Patients should not consume food beginning 1 hour before and ending 1 hour after taking study drug.

Study Schedule 1: Assessments for Parts A, B, C, D, E, F, and G (Concluded)

- g Imaging studies are performed locally. Radiological tumor assessment is performed at baseline (Day -28 to Day-4), then between Day 21 and Day 28 (inclusive) of every other cycle beginning with Cycle 2; if necessary, radiological tumor assessment between Day 21 and Day 28 may be extended to Day 29 or Day 30 if the Day 28 procedures occur on Day 29 or Day 30, respectively (refer to footnote p for additional information). For patients with glioblastoma multiforme who are receiving corticosteroids (for example, dexamethasone), the baseline imaging study should be performed on a stable dose of corticosteroids. For patients with glioblastoma multiforme or brain metastases, radiological tumor assessment should also include MRI scan (preferred) or CT scan of the brain.
- h If a patient is discontinued from the study, repeat radiology may be omitted if progressive disease can be documented quantitatively with clinical measurements.
- i Request archived paraffin-embedded tumor tissue (to be used for assessment of tumor Rb and p-Rb status), but only after study eligibility is confirmed.
- j Only for patients in Parts B, C, D, E, F, and G. Pre-treatment biopsy should be obtained (whenever clinically feasible) between Day -14 and Day -4, but only after study eligibility is confirmed. Posttreatment biopsy should be obtained (whenever clinically feasible) between Day 8 and Day 22. Greater flexibility has been provided for the post-treatment tumor biopsy (15 ± 7) compared to other Day 15 assessments (15 ± 2) to enable radiographic guidance and access to appropriate medical specialists.
- k For central versus local labs, refer to [Attachment 2](#).

- o Follow-up starts just after the last dose of study drug and ends when final safety assessments are completed (30 ± 7 days after last dose of study drug).
- p If Day 28 procedures occur on Day 29 or 30, then these procedures are included in the current cycle and initiation of the next cycle is delayed until the following day.
- q For patients already receiving fulvestrant at time of study entry, fulvestrant dose on Cycle 1 Day 1 should correspond approximately to the date of its expected monthly administration.
- r For patients already receiving fulvestrant at time of study entry, fulvestrant should not be administered on Cycle 1 Day 15.

Continued Access Assessments

| Cycle/Visit | Cycles 501-5XX | | Continued Access Follow-up (901) | Comments |
|---|----------------|-------|----------------------------------|---|
| Relative Day Within Cycle | 1 to 27 | 28 ±2 | | |
| Adverse Events Collection/CTCAE Grading | | X | X | All AEs and SAEs will be reported on the CRF. |
| LY2835219 Therapy | X | X | | LY2835219 is to be administered according to Section 6.2.1. Study drug exposure will be reported on the CRF. |
| Fulvestrant Therapy (Part G only) | | X | | Fulvestrant (Part G) is to be administered according to Section 6.2.1. Study drug exposure will be reported on the CRF. |

Abbreviations: AE = adverse event; CRF = case report form; CTCAE = Common Terminology Criteria for Adverse Event; SAE = serious adverse event.

Note: Efficacy and laboratory assessments will be done at the investigator's discretion based on the standard of care.

Attachment 2. Protocol JPBA Clinical Laboratory Tests

Clinical Laboratory Tests

Hematology^a

Hemoglobin
Hematocrit
Erythrocyte count (RBC)
Mean cell volume (MCV)
Mean cell hemoglobin concentration (MCHC)
Leukocytes (WBC)
Neutrophils (segmented + bands)
Lymphocytes
Monocytes
Eosinophils
Basophils
Platelets
Reticulocyte count^a (central only)

Clinical Chemistry^a (except as indicated)

Serum Concentrations of:
Sodium
Potassium
Bicarbonate^b (local only)
Chloride
Glucose (random)

Calcium
Albumin
Total Protein
Blood Urea Nitrogen (BUN)
Creatinine
Alkaline Phosphatase
Alanine Aminotransferase (ALT)
Aspartate Aminotransferase (AST)
Total Bilirubin and Direct Bilirubin
Creatine Kinase (CK) Total
Lactate Dehydrogenase (LDH)
Uric Acid

Serum Pregnancy Test (females only)^b (local only)

Special Blood Tests^a (central only)

Serum Cortisol (random)
Lymphocyte Subset Analysis (CD3, 4, 8, and 19)

Abbreviations: RBC = red blood cells; WBC = white blood cells; INR = International Normalized Ratio.

^a Assayed by Lilly-designated (central) laboratory.

^b Assayed by investigator-designated (local) laboratory.

Attachment 3. Protocol JPBA Recommended Hepatic Monitoring Tests for Treatment Emergent Abnormality

| Hepatic Hematology^a | Haptoglobin^a |
|---------------------------------------|--|
| Hemoglobin | |
| Hematocrit | |
| RBC | Hepatic Coagulation^a |
| WBC | Prothrombin Time |
| Neutrophils, segmented | Prothrombin Time, INR |
| Lymphocytes | |
| Monocytes | Hepatic Serologies^{a,b} |
| Eosinophils | Hepatitis A antibody, total |
| Basophils | Hepatitis A antibody, IgM |
| Platelets | Hepatitis B surface antigen |
| | Hepatitis B surface antibody |
| | Hepatitis B Core antibody |
| Hepatic Chemistry^a | Hepatitis C antibody |
| Total bilirubin | Hepatitis E antibody, IgG |
| Direct bilirubin | Hepatitis E antibody, IgM |
| Alkaline phosphatase | |
| ALT | Anti-nuclear antibody^a |
| AST | |
| GGT | Anti-smooth muscle antibody^a |
| CPK | |

Abbreviations: ALT = alanine aminotransferase; AST = aspartate aminotransferase; CPK = creatine phosphokinase; GGT = gamma glutamyl transferase; Ig = immunoglobulin; INR = International Normalised Ratio; RBC = red blood cells; WBC = white blood cells.

^a Assayed by local laboratory.

^b Reflex/confirmation dependent on regulatory requirements and/or testing availability.

Attachment 4. Protocol JPBA
Pharmacokinetic and Pharmacodynamic Sampling Schedule

| PK Sample Number | Day in Cycle 1 | LY 2835219 Dosing | Sampling Time for PK from blood (LY2835219) ^a | Sampling Time for PK from CSF (LY2835219) ^a (Parts B, C, D, E, F only) |
|------------------|----------------|-------------------|--|--|
| | -14 to -4 | | | |
| 1 | -3 | X | Pre-dose (0 h) | Pre-dose (0 h) ^d |
| 2 | -3 | | 1 h \pm 10 min post-dose | |
| 3 | -3 | | 2 h \pm 10 min post-dose | |
| 4 | -3 | | 4 h \pm 20 min post-dose | |
| 5 | -3 | | 6 h \pm 20 min post-dose | |
| 6 | -3 | | 8 h \pm 20 min post-dose | |
| 7 | -3 | | 10 h \pm 20 min post-dose ^e | |
| 8 | -2 | No dose | 24 \pm 2 h post-dose | |
| 9 | -1 | No dose | 48 \pm 2 h post-dose | |
| 10 | 1 | X | Pre-dose | |
| 11 | 15 | X | Pre-dose (0 h) | |
| 12 | 15 | | 1 h \pm 10 min post-dose | |
| 13 | 15 | | 2 h \pm 10 min post-dose | |
| 14 | 15 | | 4 h \pm 20 min post-dose | 4 h post-dosed |
| 15 | 22 | X | Pre-dose (0 h) | |
| 16 | 28 | X | Pre-dose (0 h) | |
| 17 | 28 | | 1 h \pm 10 min post-dose | |
| 18 | 28 | | 2 h \pm 10 min post-dose | |
| 19 | 28 | | 4 h \pm 20 min post-dose | |
| 20 | 28 | | 6 h \pm 20 min post-dose | |
| 21 | 28 | | 8 h \pm 20 min post-dose | |
| 22 | 28 | | 10 h \pm 20 min post-dose ^e | |
| 23 | 29 | No dose | 24 \pm 2 h post-dose | |

CCI

Pharmacokinetic and Pharmacodynamic Sampling Schedule (Concluded)

Abbreviations: CSF = cerebrospinal fluid; h or hrs = hours; min = minutes; PD = pharmacodynamic; PK = pharmacokinetic.

a Samples of approximately 2 mL of whole blood will be drawn to measure concentrations of fulvestrant (Part G only), LY2835219, and its metabolites. concentrations. For Part G, the pre-dose PK samples on Days 1, 15, 22, and 28 will also be used to measure concentrations of fulvestrant. Samples of approximately 2 mL of cerebrospinal fluid will be drawn for measurement of LY2835219 and its metabolites. If a patient does not take the LY2835219 dose on a day with PK sampling, then it does not constitute a protocol violation to omit collection of the “post-dose” PK samples for that day.

CCI

For dose confirmation (Parts B, C, D, E, F and G) only, patients with glioblastoma multiforme or brain metastases should have lumbar puncture at these time points (whenever clinically feasible) with collection of approximately 2ml of cerebrospinal fluid for measurement of LY2835219. To provide flexibility for patients and study personnel, the baseline (pre-dose) sample on Day -3 may be obtained before the first dose of study drug from Day -14 through Day -3; the sample (4 h post-dose) on Day 15, though preferably obtained at approximately the same time as a corresponding plasma PK sample, may be obtained 2 to 8 hours post-dose. In no instance should the timing of other PD or blood PK samples be compromised due to constraints associated with collection of the CSF sample. Omission of CSF samples (for example, not clinically feasible) will not constitute a protocol violation.

c If patient constraints preclude collection of this 10-hour PK sample, omission of this sample will not constitute a protocol violation.

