6.2.1. Dosing Schedule

For the once daily schedule, patients will continue to receive LY2835219 orally every 24 hours (± 3 hours) for Days 1 through 28 of a 28-day cycle. For the twice daily schedule, patients will receive LY2835219 orally every 12 hours (± 3 hours) for Days 1 through 28 of a 28-day cycle. For both schedules, there are modifications during Cycle 1 to enable PK sampling following a single dose and repeated doses.

During Cycle 1 on the twice daily schedule, the initial dose of study drug will be taken on Day -3 to enable PK sampling over 72 hours following a single dose; the remaining 55 doses will be taken every 12 hours on Days 1 to 28, with PK sampling on Day 1 and Day 15 and over 24 hours following the single dose taken on Day 28. For Cycle 1, patients should be specifically instructed not to take a second dose of study drug on Day 28; if such a dose is inadvertently taken on Day 28, it constitutes a protocol violation. Patients should not consume food beginning 1 hour before and ending 1 hour after taking study drug.

During Cycle 2 and beyond on the twice daily schedule, study drug is taken orally every 12 hours on Days 1 through 28 of a 28-day cycle.

During all cycles, study drug should be taken at approximately the same time(s) each day. If a patient misses or vomits a dose, that dose should be omitted. Patients must record the time and amount of each dose taken (or alternatively, the time and amount of the dose missed or vomited) in a daily diary.

For Part G, patients should receive fulvestrant according to the study schedule. For patients already receiving fulvestrant at time of study entry, the fulvestrant dose on Cycle 1 Day 1 should correspond approximately to the expected date for its monthly administration and fulvestrant should not be administered on Cycle 1 Day 15.

For Part G, fulvestrant 500 mg should be administered intramuscularly into the buttocks slowly (1 to 2 minutes per injection) as two 250-mg injections, one in each buttock; however, for patients with moderate hepatic impairment (defined as Child-Pugh Class B), fulvestrant 250 mg should be administered intramuscularly into the buttock slowly (1 to 2 minutes) as one 250-mg injection.

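### The only readable purpose of the pre-dose lumbar puncture is to measure a drug not yet given, so it adds nothing to the estimate of CSF exposure

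*Protocol*

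**What the plan says.** The Attachment 4 sampling table has two CSF entries. One is at 0 h before the dose on Day -3. The other is 4 h after the dose on Day 15, which the CSF footnote relaxes: it "may be obtained 2 to 8 hours post-dose". Attachment 1 carries both under the row label "CSF PK Sampling".

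- **Who is asked.** The CSF footnote says that "patients with glioblastoma multiforme or brain metastases should have lumbar puncture at these time points (whenever clinically feasible".
- **When the first sample is taken.** The same footnote adds that "the baseline (pre-dose) sample on Day -3 may be obtained before the first dose of study drug from Day -14 through Day -3".
- **What it is for.** Footnote a of Attachment 4: "Samples of approximately 2 mL of cerebrospinal fluid will be drawn for measurement of LY2835219 and its metabolites". The CSF footnote: "with collection of approximately 2ml of cerebrospinal fluid for measurement of LY2835219".
- **When dosing starts.** Protocol 6.2.1, for the twice daily schedule used in the expansions: "the initial dose of study drug will be taken on Day -3".
- **How binding it is.** "Omission of CSF samples (for example, not clinically feasible) will not constitute a protocol violation".

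**The concern.** A pre-dose concentration is informative when earlier doses have been given, as with the plasma samples on Days 15, 22 and 28. Before the first dose there is no drug exposure to characterize. In plasma, a redundant first sample costs about 2 mL of blood. In CSF, it costs a lumbar puncture in a patient with a brain tumor or brain metastases.

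The scientific question is a fair one. Protocol 4.1 gives brain distribution as a reason for interest in this compound, and CSF concentration on treatment bears on it. What is at stake is whether one of the two punctures requested per eligible patient serves that question, or any other question that the plan states.

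**Working it through.** The plan gives no figure to reproduce. The check sets its statements side by side.

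**1. Can drug be present?** The first dose is on Day -3, and the sample is taken before it, as early as Day -14. In a patient never given LY2835219, the expected concentration of parent and metabolites is zero.

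The protocol does not name earlier LY2835219 use as an exclusion. Criteria [7] and [13] require 14 days off a nonmyelosuppressive agent, or 21 days off a myelosuppressive one, before the first dose. Protocol 4.6.3 gives animal half-lives of about 6 to 17 hours. Assume, for lack of a human value, that the longest applies, in CSF as in plasma. The fraction left is 0.5^(hours / 17).

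- 14-day rule, sample on Day -3: 14 × 24 = 336 h; 0.5^(336/17) ≈ 1.1 × 10^-6.
- 21-day rule, sample on Day -14, which is 11 days before the first dose: (21 − 11) × 24 = 240 h; 0.5^(240/17) ≈ 5.6 × 10^-5.
- 14-day rule, sample on Day -14: (14 − 11) × 24 = 72 h; 0.5^(72/17) ≈ 0.05.

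Protocol 4.6.5 expects myelosuppression from this drug, so the 21-day rule is the likelier one. Only the unusual combination of previous LY2835219 treatment, the shorter rule and the earliest sampling day leaves a noticeable residue. Even that would describe earlier treatment, not CSF exposure in this study.

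**2. What does each sample contribute to CSF exposure?** The Day 15 sample gives an on-treatment concentration and is preferably drawn near a plasma sample, so the two can be compared. The baseline sample contributes an expected zero. Subtracting it changes nothing unless the assay reads background in CSF.

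**3. Does any visible analysis use it?**

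- Protocol 7.2.1 describes the validated LC/MS/MS assay under plasma samples and does not mention CSF.
- Protocol 9.1.5 and 9.1.7 and SAP 6.3.6 and 6.3.8 concern plasma data or LY2835219 PK in general.
- SAP Appendix 2 lists LY2835219 PK concentrations and a urine concentration listing, but no CSF output by name.
- Protocol Table JPBA.4.1 and section 7.2.2 name hair follicles, skin and tumor as pharmacodynamic tissues, not CSF.

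**4. How many punctures?** Two are scheduled per eligible patient and the proposal removes one. Part C, where every patient has glioblastoma, plans at least 15 and up to 60. If a fraction f of n patients would have had the baseline puncture, the number avoided is n × f. With f anywhere from 0 to 1, that is 0 to 15 at the minimum size and 0 to 60 at the maximum. The documents give neither f nor the number of patients with brain metastases in the other parts.

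**The case against.** The strongest reply is that a true concentration of zero is not a measured zero. A patient's own pre-dose CSF can show matrix interference or assay background. That could matter here, because the readable text describes a validated method for plasma only. The plan also takes a plasma sample before the first dose, so the CSF baseline follows its own convention. This part stands: a reader might infer that the puncture yields no information because the answer is zero by definition, and the documents do not support that. The plan never states the blank as a purpose, however, and checking an assay for interference does not obviously need a puncture from every eligible patient.

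The second reply is redaction. Both footnotes attached to the CSF row of Attachment 1 (l and m) are missing, as are Protocol 9.1.6 and SAP 6.3.7 on pharmacodynamics. No pharmacodynamic columns are visible in Attachment 4, although its title covers them. A further use of baseline CSF could sit there, so a sole purpose can be asserted only for the readable text. The CSF footnote itself is readable, though, and states drug measurement.

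The third reply is that sampling is optional, that omission is no violation, and that the Day -14 to Day -3 window eases the burden. This reduces the number of punctures but supplies no purpose for those that are done.

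Finally, nothing here affects the primary objective or biases an estimate. That is correct; the point concerns procedural burden.

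**Conclusion.** The point holds for the readable text. The baseline puncture is requested to measure a drug and metabolites not expected to be present, and it adds nothing to the PK estimate of CSF exposure, which comes from the Day 15 sample. At most it is a per-patient assay blank, with no visible analysis attached.

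The size is at most one puncture per eligible patient. The total is unknown. Reading the Part C enrolment of 15 to 60 as a count of avoidable punctures would assume that every patient has an optional procedure. A reader might also infer that the first puncture makes patients less willing to have the second; that is plausible, but nothing in the documents shows it.

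The conclusion assumes no earlier LY2835219 treatment, or an adequate washout from it, and no other use of baseline CSF in the redacted text. Confidence is therefore moderate.

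**What to change.** Remove the pre-dose CSF sample from Attachment 4 (row 1 of the table and the baseline wording in the CSF footnote) and from the CSF row of Attachment 1. Keep the Day 15 sample and its window. If redacted text already gives the baseline CSF another planned use, the sample can stay, and the CSF footnote should name that use and the analysis that draws on it.

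In the same edit, reconcile who is sampled: the Attachment 4 column heading limits CSF to Parts B to F, while the CSF footnote also includes Part G.

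The cost is a short wording amendment and the loss of a per-patient CSF blank. Drug-free CSF from another source could replace it for checking the assay, though it would not be patient-specific. The change helps only patients not yet sampled, and the documents do not say whether enrolment is still open.
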